## 2 OVERVIEW

The following describes the Statistical Analysis Plan (SAP) for the analysis of safety data from HVTN 303 for Safety Monitoring Board (SMB) reports and the Final Study Report (FSR) for Safety.

## 3 PROTOCOL SUMMARY

### 3.1 Title

A Phase 1, Open-Label Clinical Trial to Evaluate Safety, Tolerability, and Immunogenicity of Adjuvanted HIV-1 Fusion Peptide Vaccine (VRC- HIVVCP0108-00-VP) Alone or in Prime-Boost Regimens with Adjuvanted HIV-1 Envelope Trimer 4571 (VRC-HIVRGP096-00-VP) and HIV-1 Trimer 6931 (VRC-HIVRGP0106-00-VP) Vaccines in Healthy Adults.

### 3.2 Design

This is a phase 1, open-label, dose-escalation study to evaluate the dose, safety, tolerability and immunogenicity of adjuvanted HIV-1 Fusion Peptide (FP) conjugate vaccine (FP8v1-rTTHC) alone or in prime-boost regimens with adjuvanted HIV-1 Trimer 4571 and adjuvanted HIV-1 Trimer 6931. The primary hypothesis is that FP8v1-rTTHC, HIV-1 Trimer 4571, and HIV-1 Trimer 6931 adjuvanted vaccines are safe and tolerable when administered alone and when co-administered with HIV-1 Trimer 4571, in prime-boost regimens.

### 3.3 Study products

- FP8v1-rTTHC (FP conjugate vaccine) is an HIV-1 fusion peptide conjugated to recombinant tetanus toxoid heavy chain fragment C (rTTHC) via sulfo-SIAB chemical linker. FP8v1 corresponds to the amino-terminal eight residues of the most prevalent HIV fusion peptide sequence. FP conjugate vaccine will be provided at a 1-milligram (mg)/milliliter (mL) concentration in 3-mL glass vials filled to 0.7 mL.
- HIV-1 Trimer 4571 (Trimer 4571) is a synthetic soluble HIV-1 envelope product that consists of an HIV-1 envelope (Env) trimer variant, derived from clade A, strain BG505. Trimer 4571 is provided at a 500-mcg/mL concentration in 3-mL glass vials filled to 1.2 mL
- HIV-1 Trimer 6931 (Trimer 6931) is a synthetic soluble HIV-1 envelope product that consists of an HIV-1 envelope (Env) trimer variant, derived from consensus clade C sequence (ConC). Trimer 6931 will be provided at a 1-mg/mL concentration in 3-mL glass vials filled to 1.2 mL
- Adjuplex is the adjuvant and will be provided in a sterile, pyrogen-free, homogeneous suspension at 0.7 mL in 3-mL glass vials. Adjuplex will be mixed with study products in the pharmacy during preparation prior to vaccination at a 20% dose by volume
- PBS (labeled as Phosphate Buffered Saline pH 7.2): Diluent

### 3.4 Study population

Healthy adults aged 18 to 50 years, inclusive

### 3.5 Study plans and schema table

This study has two parts. Part A will evaluate the safety, tolerability, and immunogenicity of single doses of the FP conjugate, Trimer 4571 and Trimer 6931 vaccines, in a dose-escalation design. Each product must be assessed as safe prior to use in Part B. Trimer 4571 with alum adjuvant has been previously evaluated in humans but will be tested in Part A with Adjuplex. Part B will evaluate the safety, tolerability, and immunogenicity of FP conjugate prime, Trimer 4571 prime, or an FP plus Trimer 4571 prime, all followed by subsequent doses of Trimer 4571, Trimer 6931 and both Trimmers combined. Study vaccines will be administered intramuscularly (IM) via needle and syringe in two injection sites. The study schema is below:

**Table 2-1 Schema**

Part A: Dose Escalation**											
Group	N	W0									
1	3	25 mcg FP conjugate vaccine									
2	3	200 mcg FP conjugate vaccine									
3	3	100 mcg Trimer 6931									
4	3	200 mcg Trimer 6931									
5	3	200 mcg Trimer 4571									
Part A Total	15*										
Part B: Prime Boost Regimen**											
Group	N	W0	W4	W8***	W12***	W20***	W24***	W32***	W36***	W44***	W48***
6	15 10	200 mcg Trimer 4571			200 mcg Trimer 4571		200 mcg Trimer 6931		100 mcg Trimer 4571 + 100 mcg Trimer 6931		100 mcg Trimer 4571 + 100 mcg Trimer 6931
7	15 10	200 mcg FP conjugate vaccine	200 mcg FP conjugate vaccine	200 mcg FP conjugate vaccine	200 mcg Trimer 4571		200 mcg Trimer 4571		200 mcg Trimer 6931		100 mcg Trimer 4571 + 100 mcg Trimer 6931
8	15 9	200 mcg FP conjugate vaccine + 200 mcg Trimer 4571	200 mcg FP conjugate vaccine + 200 mcg Trimer 4571	200 mcg FP conjugate vaccine + 200 mcg Trimer 4571		200 mcg Trimer 6931		100 mcg Trimer 4571 + 100 mcg Trimer 6931		100 mcg Trimer 4571 + 100 mcg Trimer 6931	
Part B total	45\$ 29										
Overall Total	60# 44										

**Table 1-1 Footnotes:**

\*\*Adjuplex adjuvant will be mixed with all study products in Part A and Part B at 20% by volume in the pharmacy during product preparation for all vaccinations. Once mixed, all study injections will be divided into 2 syringes, and each syringe will be administered intramuscularly to one of the deltoids.

\* In Part A, up to 20 participants may be enrolled if needed for safety or immunogenicity evaluations. Additional participants may be enrolled to ensure the availability of 2-week safety data from at least 3 participants per group.

§ In Part B, up to 50 participants may be enrolled if needed for safety or immunogenicity evaluations. Additional participants may be enrolled to ensure the availability of 2-week safety data from at least 15 participants per group.

† Total up to 70 participants can be enrolled if needed for safety or immunogenicity evaluations.

**Notes:**

\*\*\*Vaccination in Part B starting from Week 8 onwards did not take place.

Actual Ns for Group 6, 7 and 8 were 10, 10 and 9 respectively. In Part B total 29 participants were enrolled

Part A of the study may begin with direct enrollment of participants into the following groups simultaneously:

- Group 1 with no more than 1 participant enrolled per day for the 3 participants.
- Group 3 with no more than 1 participant enrolled per day for the 3 participants.

After Groups 1 and 3 have been fully enrolled, the study will be placed on a safety hold. No additional enrollments will proceed until the Protocol Safety Review Team (PSRT) has determined it is safe to do so. Once all of the reactogenicity and 2-week safety data from at least 6 participants have been submitted to the database, the PSRT must assess the accumulated product-specific data as showing no significant safety concerns before proceeding with enrollment of Groups 2, 4 and 5. If the PSRT has determined it is safe to proceed after reviewing data from Groups 1 and 3, the following groups may begin simultaneously:

- Group 2 with no more than 1 participant enrolled per day for the 3 participants
- Group 4 with no more than 1 participant enrolled per day for the 3 participants
- Group 5 with no more than 1 participant enrolled per day for the 3 participants

Once Groups 2, 4 and 5 have been fully enrolled, the study will be placed on a safety hold before proceeding with Part B. Once all of the reactogenicity and 2-week safety data from at least 9 participants have been submitted to the database, the PSRT must assess the accumulated product-specific data as showing no significant safety concerns before proceeding with enrollment of Part B.

Part B enrollments may only proceed if no safety concerns have been identified for any of the product administrations in Part A of the study.

If at any time there is insufficient data to conduct a formal PSRT Safety Review because of participant discontinuations from the study before sufficient data are collected, then additional participants may be enrolled into that group to acquire the requisite data on the required number of participants specified above. Moreover, the PSRT may recommend additional participants be enrolled into a given treatment group if additional safety evaluations are requested.

Consultation with the HVTN Safety Monitoring Board (SMB), Institutional Review Board (IRB) and Food and Drug Administration (FDA), if needed, as specified by study pause criteria (per Section 9.5.1), will occur if indicated.

### 3.6 Duration per participant

For participants in Part A (Groups 1-5): 52 weeks of scheduled clinic visits

~~For participants in Part B (Groups 6 and 7): 100 weeks of scheduled clinic visits~~

~~For participants in Part B (Group 8): 96 weeks of scheduled clinic visits~~

On January 13, 2023, a protocol memo was distributed informing the clinical research sites that all vaccinations in HVTN 303 were permanently discontinued. Procedures specified for remaining follow-up visits have been revised. Duration for Part A participants remained unchanged. Duration for Part B participants (for Groups 6 -8) is 56 weeks.

### **3.7 Estimated total study duration**

~~Total study duration is 36 months (includes enrollment, planned safety holds and follow-up).~~

Following cessation of vaccination and reduction of follow-up duration the estimated total study duration is reduced to approximately 18 months.

### **3.8 Study Sites**

HVTN Clinical Research Sites (HVTN CRSs) to be specified in the Site Announcement Memo.

## **4 SAFETY OBJECTIVES AND ENDPOINTS**

*Primary objective 1:*

To evaluate the safety and tolerability of the following regimens in healthy adults:

- Adjuvanted FP conjugate vaccine administered IM at a dose of 25 or 200 mcg,
- Adjuvanted Trimer 6931, administered IM at a dose of 100 or 200 mcg,
- Adjuvanted Trimer 4571 administered IM at 200 mcg, or
- Prime-boost vaccination regimens of FP conjugate, Trimer 4571, and Trimer 6931 vaccines.

*Primary endpoint 1:*

Local and systemic reactogenicity signs and symptoms, laboratory measures of safety, and adverse and serious adverse events.

SAEs, medically attended adverse events (MAAEs), adverse events of special interest (AESIs) and AEs leading to early participant withdrawal or permanent discontinuation which will be collected throughout the study and for 12 months following any receipt of study product. Additionally, all adverse events will be collected for 28 days after any receipt of study vaccination. All safety lab related adverse events will be collected throughout duration of study.

## **5 COHORT DEFINITION**

Recruitment will target 60 (up to 70) healthy adult participants 18 to 50 years of age. However, due to the early termination, the study enrolled a total of 44 participants (15 in Part A and 29 in Part B). The primary goal of this study is to identify safety concerns that may be associated with the study products.

Since enrollment is concurrent with receiving the first study vaccination, all enrolled participants will provide some safety data. For immunogenicity analyses, the sample calculations are based on the available samples..

## **6 POTENTIAL CONFOUNDERS**

Characterization of the safety of the vaccine is susceptible to confounding by adverse events not related to the vaccine that by chance occur more often in one arm of the trial than another. Therefore analyses involving adverse events will incorporate the reported relationship to product as assessed by HVTN staff.

## **7 RANDOMIZATION**

In Part A, Groups 1 and 3 will be randomized and will enroll no more than 1 participant per day for 3 participants per group. Contingent on the safety data from Groups 1 and 3, Groups 2, 4, and 5 will be randomized and may enroll simultaneously with no more than 1 participant per day for 3 participants for each group. Contingent on the safety data from Groups 1-5 in Part A, Groups 6-8 in Part B will be randomized and stratified by whether or not participants will be willing to consent to leukapheresis. A maximum of 7 participants per group that do NOT consent to leukapheresis collection will be enrolled. A participant's randomization assignment will be computer generated and provided to the HVTN CRS pharmacist through a Web-based randomization system. At each institution, the pharmacist with primary responsibility for dispensing study products is charged with maintaining security of the treatment assignments (except in emergency situations as specified in the HVTN manual of procedures [MOP]).

## **8 BLINDING**

Participants and site staff will be unblinded to participants' group assignments. Laboratory program staff will be unblinded to whether a sample is from Part A or Part B but will remain blinded to the treatment assignment within Part A or Part B during assay analysis.

## **9 SAMPLE SIZE**

The goal of the safety evaluation for this study is to identify safety concerns associated with product administration. The ability of the study to detect SAEs can be expressed by the true event rate above which at least 1 SAE would likely be observed and the true event rate below which no events would likely be observed. Specifically, for each vaccine arm of the study ( $n = 3$ ) in Part A, there is a 90% chance of observing at least 1 event if the true rate of such an event is 53.6% or more; and there is a 90% chance of observing no events if the true rate is 1% or less. For a vaccine arm in Part B ( $n = 9$  or 10), there is a 90% chance of observing at least 1 event if the true rate of such an event is 22.6% or 20.6% or more; and there is a 90% chance of observing no events if the true rate is 1% or less. For a combined vaccine arm (Groups 1-5 in Part A and Groups 6-8 in Part B) of the study ( $n = 44$ ), there is a 90% chance of observing at least 1 event if the true rate of such an event is 5.1% or more; and there is a 90% chance of observing no events if the true rate is 0.2% or less. As a reference, in HVTN vaccine trials from April 2008 through March 2018, about 1.7% of participants who received placebos experienced an SAE.

Binomial probabilities of observing 0, 1 or more, and 2 or more events among arms of size 3, 9, 10, and 44 are presented in Table 6-1 for a range of possible true adverse event rates. These calculations provide a more complete picture of the sensitivity of this study design to identify potential safety problems with the vaccine.

**Table 6-1 Probability of observing 0 events, 1 or more events, and 2 or more events, among arms of size 3, 9, 10, and combined arms of size 44, for different true event rates**

True event rate (%)	Pr(0/3)	Pr(1+3)	Pr(2+3)	Pr(0/10)	Pr(1+/10)	Pr(2+/10)	Pr(0/9)	Pr(1+/9)	Pr(2+/9)	Pr(0/44)	Pr(1+/44)	Pr(2+/44)
1	97	3	0	90.4	9.6	0.4	91.4	8.6	0.3	64.3	35.7	7.2
4	88.5	11.5	0.5	66.5	33.5	5.8	69.3	30.7	4.8	16.6	83.4	53
5	85.7	14.3	0.7	59.9	40.1	8.6	63	37	7.1	10.5	89.5	65.3
10	72.9	27.1	2.8	34.9	65.1	26.4	38.7	61.3	22.5	1	99	94.3
20	51.2	48.8	10.4	10.7	89.3	62.4	13.4	86.6	56.4	<0.1	>99.9	99.9
30	34.3	65.7	21.6	2.8	97.2	85.1	4	96	80.4	<0.1	>99.9	>99.9
40	21.6	78.4	35.2	0.6	99.4	95.4	1	99	92.9	<0.1	>99.9	>99.9
50	12.5	87.5	50	0.1	99.9	98.9	0.2	99.8	98	<0.1	>99.9	>99.9
60	6.4	93.6	64.8	0	>99.9	99.8	0	>99.9	99.6	<0.1	>99.9	>99.9

An alternative way of describing the statistical properties of the study design is in terms of the 95% confidence interval (CI) for the true rate of an adverse event based on the observed data. Table 6-2 shows the 2-sided 95% confidence intervals for the probability of an event based on a particular observed rate. Calculations are done using the score test method (52). If none of the participants in a group of size of 3 (eg, Groups 1-5 in Part A) or in a group of size of 9 or 10 (eg, the Groups 6-8 in Part B) are experiencing a safety event, the 95% 2-sided upper confidence bound for the true rate of such events in the total vaccinated population is 56.1% or 29.9% or 29.2%, respectively. For the combined vaccine arms in Part A and Part B (Groups 1-8, n = 44), the 95% 2-sided upper confidence bound for this rate is 9.8%.

**Table 6-2 Two-sided 95% confidence intervals based on observing a particular rate of safety endpoints for arms of size 3, 9, 10 or combined arms of size 44**

Observed event rate	95% Confidence interval (%)
0/3	[0, 56.1]
1/3	[6.1, 79.2]
2/3	[20.8, 93.9]
0/9	[0, 29.9]
1/9	[2, 43.5]
2/9	[6.3, 54.7]
0/10	[0, 29.2]
1/10	[0.1, 30.5]
2/10	[0.2, 31.9]
0/44	[0.1, 9.8]
1/44	[0.3, 11.4]
2/44	[0.6, 12.9]

## 10 STATISTICAL ANALYSIS

### 10.1 Statistical analyses

This section describes the final study analyses, unblinded as to treatment arm assignment. All data from enrolled participants will be analyzed according to the initial randomization assignment regardless of how many vaccinations they received. In the rare instance that a participant receives the wrong treatment at a specific vaccination time, the Statistical Analysis Plan (SAP) will address how to analyze the participant's safety data. Analyses are modified intent-to-treat in that individuals who are randomized but not enrolled do not contribute data and hence are excluded. Because of the brief length of time between randomization and enrollment (typically no more than 4 working days), very few such individuals are expected.

Analyses for primary endpoints will be performed using statistical analysis system (SAS) and R. All other descriptive and inferential statistical analyses will be performed using SAS, StatXact, or R statistical software.

No formal multiple comparison adjustments will be employed for multiple safety endpoints, multiple primary immunogenicity endpoints, or secondary endpoints. However, multiplicity adjustments will be made for certain immunogenicity assays, as discussed below, when the assay endpoint is viewed as a collection of hypotheses (eg, testing multiple peptide pools to determine a positive response).

### 10.2 Analysis variables

The analysis variables consist of baseline participant characteristics, safety, and immunogenicity for primary- and secondary-objective analyses.

### **10.3 Baseline comparability**

Treatment arms will be compared for baseline participant characteristics using descriptive statistics.

### **10.4 Safety/tolerability analysis**

Since enrollment is concurrent with receiving the first vaccination, all participants will have received at least 1 vaccination and therefore will provide some safety data.

#### **10.4.1 Reactogenicity**

The number and percentage of participants experiencing each type of reactogenicity sign or symptom will be tabulated by severity and treatment arm in Part A and Part B and the percentages displayed graphically by arm. For a given sign or symptom, each participant's reactogenicity will be counted once under the maximum severity for all injection visits. In addition, to the individual types of events, the maximum severity of local pain or tenderness, induration or erythema, and of systemic symptoms will be calculated. Kruskal-Wallis tests will be used to test for differences in severity across arms and Wilcoxon rank sum test will be used to test for difference in severity between 2 arms in Part B.

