HIV VACCINE
TRIALS NETWORK

PROTOCOL

HVTN 303

A Phase 1, Open-Label Clinical Trial to Evaluate Safety, Tolerability, and Immunogenicity of Adjuvanted HIV-1 Fusion Peptide Conjugate Vaccine (VRC-HIVVCP0108-00-VP) Alone or in Prime-Boost Regimens with Adjuvanted HIV-1 Envelope Trimer 4571 (VRC-HIVRGP096-00-VP) and HIV-1 Trimer 6931 (VRC-HIVRGP0106-00-VP) Vaccines in Healthy Adults

DAIDS DOCUMENT ID 38835

IND 028412 HELD BY DAIDS

CLINICAL TRIAL SPONSORED BY

Division of AIDS (DAIDS)
National Institute of Allergy and Infectious Diseases (NIAID)
National Institutes of Health (NIH)
Department of Health and Human Services (DHHS)
Bethesda, Maryland, USA

STUDY PRODUCTS PROVIDED BY

Vaccine Research Center (VRC)
NIAID, NIH, DHHS
Bethesda, Maryland, USA

September 21, 2023

Final
HVTN 303
Version 2.0

HVTN 303 enrolled (vaccinated) its first participant on August 15, 2022, with the goal to enroll 60 participants in the study. As of Dec 20, 2022, 44 participants were enrolled (no enrollments occurred after this date). Part A (Groups 1, 2, 3, 4, and 5) completed enrollment of 15 participants from August 15 to October 14, 2022.

Part B enrolled 29 participants from November 3 to December 20, 2022: Group 6 enrolled 10 ppts, all of whom received 1 vaccination; Group 7 enrolled 10 participants, 5 of whom received 2 vaccinations; Group 8 enrolled 9 participants, 6 of whom received 2 vaccinations. No participants received a 3rd vaccination.

Over time, the PSRT observed trends in local and systemic reactogenicity (grade 3 fever, grade 3 injection site erythema, and/or induration/swelling), unsolicited adverse events (urticaria, rash, and serum sickness), and temporary increases in absolute eosinophil counts (AECs) post-vaccination. Certain of these events resulted in pauses in all vaccinations, and the PSRT requested the HVTN Safety Monitoring Board (SMB) perform an ad hoc review of all safety data. Following this review on January 11, 2023, the SMB recommended that all vaccinations in the study be permanently discontinued, and that participants be continued in safety follow-up, and these recommendations were implemented.

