9.2.1 Expedited reporting of adverse events to DAIDS

Requirements, definitions and methods for expedited reporting of AEs are outlined in Version 2.0 (January 2010) of the *Manual for Expedited Reporting of Adverse Events* to DAIDS (DAIDS Expedited Adverse Event [EAE] Manual), which is available on the RSC website at <https://rsc.niaid.nih.gov/clinical-research-sites/manual-expedited-reporting-adverse-events-daims>.

The internet-based DAIDS Adverse Experience Reporting System (DAERS) must be used for EAE reporting to DAIDS. In the event of system outages or technical difficulties, EAEs may be submitted using the DAIDS EAE Form. This form is available on the DAIDS RSC website at <https://rsc.niaid.nih.gov/clinical-research-sites/paper-eae-reporting>.

For questions about DAERS, please contact NIAID CRMS Support at [contact]. Please note that site queries may also be sent from within the DAERS application itself.

The SAE Reporting Category will be used throughout the study. All SAEs observed in this clinical trial (including PIMMCs) that are unexpected, and judged to be related to the study products, will be reported by the NIAID/DAIDS to the FDA in accordance with 21 CFR 312.32 (IND Safety Reports). After completion of the study, the suspected unexpected serious adverse reaction (SUSAR) reporting category will be used if clinical staff becomes aware of an event on a passive basis.

The study products for which expedited reporting are required are:

- VRC-HIVVCP0108-00-VP (FP8v1-rTTHC; FP conjugate vaccine) with Adjuplex
- VRC-HIVRGP096-00-VP (Trimer 4571) with Adjuplex
- VRC-HIVRGP0106-00-VP (Trimer 6931) with Adjuplex

There is no placebo product administered in this protocol.

The NIAID/DAIDS will report all unexpected SAEs related to the study products observed in this clinical trial to the FDA in accordance with 21 CFR 312.32 (IND Safety Reports).

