#### **10.4.2 AEs and SAEs**

AEs will be summarized using Medical Dictionary for Regulatory Activities (MedDRA) System Organ Class and preferred terms. Tables will show by treatment arm (in Part A and Part B) the number and percentage of participants experiencing an AE within a System Organ Class or within preferred term category by severity or by relationship to study product. For the calculations in these tables, a participant with multiple AEs within a category will be counted once under the maximum severity or the strongest recorded causal relationship to study product. Formal statistical testing comparing arms is not planned since interpretation of differences must rely heavily upon clinical judgment.

A listing of SAEs reported to the Division of AIDS (DAIDS) Regulatory Support Center (RSC) Safety Office will provide details of the events including severity, relationship to study product, time between onset and last vaccination, and number of vaccinations received.

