#### **10.4.3 Local laboratory values**

Box plots of local laboratory values will be generated for baseline values and for values measured during the course of the study by treatment arm (Part A and Part B) and visit. Each box plot will show the first quartile, the median, and the third quartile. Outliers (values outside the box plot) will also be plotted. If appropriate, horizontal lines representing boundaries for abnormal values will be plotted.

For each local laboratory measure, summary statistics will be presented by treatment arm and time point, as well as changes from baseline for post enrollment values. In addition, the number (percentage) of participants with local laboratory values recorded as meeting Grade 1 AE criteria or above as specified in the Division of AIDS Table for Grading the Severity of Adult and Pediatric Adverse Events will be tabulated by treatment arm for each post vaccination time point. Reportable clinical laboratory abnormalities without an associated clinical diagnosis will also be included in the tabulation of AEs described above.

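### The only tests on the primary safety endpoint compare reactogenicity between arms that all received Adjuplex; they say nothing about a reaction level common to all arms, and the plan attaches no confidence interval to the observed rates.

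*SAP*

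**What the plan says.** The hypothesis is absolute. SAP 3.2 states: "The primary hypothesis is that FP8v1-rTTHC, HIV-1 Trimer 4571, and HIV-1 Trimer 6931 adjuvanted vaccines are safe and tolerable".

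The inference is comparative. For reactogenicity, SAP 10.4.1 (repeated in protocol 6.5.3.1) states: "Kruskal-Wallis tests will be used to test for differences in severity across arms and Wilcoxon rank sum test will be used", with the Wilcoxon test applied to pairs of Part B arms. The same section also provides counts and percentages of each reaction by severity and arm, with graphs.

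The other parts of the safety endpoint have no tests. On adverse events, SAP 10.4.2 says: "Formal statistical testing comparing arms is not planned since interpretation of differences must rely heavily upon clinical judgment". Laboratory values are descriptive under SAP 10.4.3: "For each local laboratory measure, summary statistics will be presented by treatment arm and time point, as well as changes from baseline".

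No arm is free of the adjuvant. The schema footnote in the SAP reads: "Adjuplex adjuvant will be mixed with all study products in Part A and Part B at 20% by volume". Protocol 9.2.1 adds: "There is no placebo product administered in this protocol".

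On Part B size, the SAP notes: "Actual Ns for Group 6, 7 and 8 were 10, 10 and 9 respectively".

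SAP section 9 (Table 6-2) gives 95% score intervals for hypothetical event counts, to describe the design. SAP 10.4.1 and the output lists in SAP section 11 do not apply an interval to any observed reaction rate. For immunogenicity, by contrast, protocol 6.5.4.1 commits to score intervals on observed response rates.

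**The concern.** The question the trial asks is how often these products cause unacceptable reactions. The tests answer another one: whether one Adjuplex-containing arm reacts more than another. If all arms react equally often, at whatever level, the null hypothesis is true.

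This matters for the final safety report, which the SAP governs. The protocol's title-page summary says the safety review team observed "trends in local and systemic reactogenicity (grade 3 fever, grade 3 injection site erythema, and/or induration/swelling" among the findings that preceded permanent discontinuation. A reader of that report will want to know how common grade 3 reactions were and how high the true rate could be. As written, the report would give percentages without precision, next to p-values that do not address the level. With 9 or 10 per arm, a non-significant p-value could also be misread as showing that the regimens are similar.

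**Working it through.** **Inputs.**
- From the documents: Part B arms of 10, 10 and 9; Part A arms of 3; Kruskal-Wallis and Wilcoxon on each participant's maximum severity grade; the score method for intervals.
- Assumed: two-sided alpha of 0.05 (stated in protocol 6.5.4.1 for immunogenicity; SAP 10.4.1 gives none), the grade distributions, the 0.5-SD shift and a 10% benchmark rate.

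**Calibration.** The documents state no power for the reactogenicity tests. The nearest figure is protocol Table 6-5 (Wilcoxon, 9 v 9, 100% response): 1.5 SD for 80% power and 1.8 SD for 90%. Simulating normal data with the exact Wilcoxon test gives 79.8% and 92.0%, so the method reproduces the table to within 2 points.

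**Same level in every arm (Kruskal-Wallis, 10/10/9).**
- All arms low (grades 0 to 3 at 70/20/8/2%): rejects 4.1%.
- Grade 3 in 30% of every arm (10/30/30/30%): rejects 5.0%.
- Grade 3 in 50% of every arm (10/20/20/50%): rejects 4.4%.
- Grade 3 in 60% of every arm (0/10/30/60%): rejects 4.6%.

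The rejection rate stays near or below alpha whatever the common level.

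**Difference between arms, Part B.**
- 0.5 SD, continuous scale: Wilcoxon power 16.4% (10 v 10) and 15.4% (10 v 9); Kruskal-Wallis with one arm shifted 15.5%. Missed: 84 to 85%.
- 0.5 SD, four-level grades, several baseline distributions: Wilcoxon power 13 to 15%. Missed: 85 to 87%. For example, 30/40/20/10% shifts to 15/36/27/22%, that is, grade 3 from 10% to 22%.
- Grade 3 of 10% v 30% (30/40/20/10% against 10/30/30/30%): power 32 to 33%. Missed: 67 to 68%.
- Wilcoxon power at 10 v 10 by shift: 0.25 SD 7%; 0.5 SD 16%; 0.75 SD 32%; 1.0 SD 51%; 1.25 SD 71%; 1.5 SD 85%. About 1.45 SD is needed for 80%.
- Cross-checks at 0.5 SD by t-test and normal approximation give 18 to 20% power, so 80 to 82% missed.

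In Part A (five arms of 3, one shifted 0.5 SD), Kruskal-Wallis power is 2.7%.

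**What an interval gives.** With zero events the score upper bound is z²/(n + z²), where z² = 3.8415.
- n = 9: 3.8415/12.8415 = 29.9%, matching Table 6-2.
- n = 10: 3.8415/13.8415 = 27.8%. Table 6-2 prints 29.2%.
- n = 29: 3.8415/32.8415 = 11.7%.

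Other Table 6-2 rows also depart from the score method: 1/10 is printed as 0.1 to 30.5 (score 1.8 to 40.4), 2/10 as 0.2 to 31.9 (5.7 to 51.0), and 0/44 as 0.1 to 9.8 (0 to 8.0).

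**Ability to exclude 10% when the true rate is 30%.**
- One arm: needs at least 3 events. P(X ≥ 3) is about 62% for n = 10 and 54% for n = 9.
- Part B pooled: 6/29 gives 9.8 to 38.4% and 7/29 gives 12.2 to 42.1%, so at least 7 are needed. P(X ≥ 7) = 81% at a true 30%, and 2% at a true 10%.

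**The case against.** The strongest reply is that the plan does not depend on these tests to find a high reaction rate. SAP 10.4.1 tabulates and graphs every reaction by severity and arm. SAP section 11 supplies reactogenicity summaries, and gives the monitoring board listings of severe reactions and of moderate or worse erythema or induration. Protocol 9.3 to 9.5 provides review by the safety team and the board, with defined triggers. None of this compares arms. A reader might infer that a rate high in every arm would go unnoticed; the documents do not support that, and the title-page summary shows the trends were seen by review and vaccination stopped. This part of the reply stands in full.

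A reader might also infer that a non-significant test would be taken as the trial's formal statement on tolerability. No section says so. Nor is any power claimed for these tests, so no stated power figure is wrong, and low power is expected in a phase 1 trial of this size.

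Pooling Part B is open to challenge: it mixes three regimens, and 18 participants with one dose with 11 who had two (5 in Group 7, 6 in Group 8), while the primary objective is by regimen. The 81% for the pooled interval should therefore not be set against the 5% for the three-arm test as if they were alternatives; the per-arm figures are 54 to 62%.

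What the reply leaves unanswered is the missing precision on the observed rates, in a plan whose protocol already requires it for immunogenicity.

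**Conclusion.** The concern holds in a limited form. The between-arm tests carry no information on a common reaction level, and this does not depend on the assumed distributions. In Part B they miss an assumed 0.5-SD difference about 85% of the time (80 to 87% across methods). The 0.5 SD, the grade distributions and alpha for these tests are assumptions, and the power range by shift size shows how far the result depends on the first.

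The gap is in reporting, not in safety monitoring. The rates will be displayed, but without the interval that would say how high each could be. Adding it is a worthwhile, inexpensive improvement to the final safety report. It does not supply a pass or fail statement on tolerability, because the documents set no acceptable rate.

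**What to change.** In SAP 10.4.1 and protocol 6.5.3.1:
- Report the number and proportion of participants with a grade 3 or higher local, and separately systemic, solicited reaction, with two-sided 95% score intervals, for each arm.
- Add Part B combined (n = 29) as a supplementary summary, noting that it mixes regimens and one- and two-dose recipients.
- Report Part B between-arm differences in proportions with 95% confidence intervals, naming the method.
- Label the Kruskal-Wallis and Wilcoxon p-values exploratory, and state that p > 0.05 is not evidence of similarity or tolerability.
- State that the grade 3 cut was chosen after the grade 3 trends were known, and keep the all-grade tables beside it.
- Do not declare tolerability from the upper bound, since no threshold is given.
- Compute the score intervals afresh instead of reading them from Table 6-2, and correct its n = 10 and n = 44 rows.

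The cost is SAP and protocol wording and a few table columns, using data already collected. The downside is that intervals at 9 to 10 per arm are wide: even zero events leaves an upper bound of 28 to 30%.
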